10.1.3 Expectedness

Adverse events can be 'Expected' or 'Unexpected.'

10.1.3.1 Expected adverse event

Expected adverse events are those that have been previously identified as resulting from administration of the agent. For the purposes of this study, an adverse event is considered expected when it appears in the current adverse event list, the Investigator's Brochure, the package insert or is included in the informed consent document as a potential risk.

Refer to Section 6.1 for a listing of expected adverse events associated with the study agent(s).

10.1.3.2 Unexpected adverse event

For the purposes of this study, an adverse event is considered unexpected when it varies in nature, intensity or frequency from information provided in the current adverse event list, the Investigator's Brochure, the package insert or when it is not included in the informed consent document as a potential risk.

10.1.4 Attribution

Attribution is the relationship between an adverse event or serious adverse event and the study treatment. Attribution will be assigned as follows:

- Definite – The AE is clearly related to the study treatment.
- Probable – The AE is likely related to the study treatment.
- Possible – The AE may be related to the study treatment.
- Unlikely - The AE is doubtfully related to the study treatment.
- Unrelated - The AE is clearly NOT related to the study treatment.

10.2 Procedures for AE and SAE Recording and Reporting

Participating investigators will assess the occurrence of AEs and SAEs at all participant evaluation time points during the study.

All AEs and SAEs whether reported by the participant, discovered during questioning, directly observed, or detected by physical examination, laboratory test or other means, will be recorded in the participant's medical record and on the appropriate study-specific case report forms.

The descriptions and grading scales found in the revised NCI Common Terminology Criteria for Adverse Events (CTCAE) version 4.0 will be utilized for AE reporting.

CONFIDENTIAL

This document is confidential. Do not disclose or use except as authorized.

Page 53 of 69

All appropriate treatment areas should have access to a copy of the CTCAE version 4.0.

A copy of the CTCAE version 4.0 can be downloaded from the CTEP website at:
http://ctep.cancer.gov/protocolDevelopment/electronic_applications/ctc.htm.

10.3 Reporting Requirements

For multi-site trials where a DF/HCC investigator is serving as the principal investigator, each participating investigator is required to abide by the reporting requirements set by the DF/HCC. The study must be conducted in compliance with FDA regulations, local safety reporting requirements, and reporting requirements of the principal investigator.

Each investigative site will be responsible to report SAEs that occur at that institution to their respective IRB. It is the responsibility of each participating investigator to report serious adverse events to the study sponsor and/or others as described below.

10.4 Reporting to the Study Sponsor

10.4.1 Serious Adverse Event Reporting

All serious adverse events that occur after the initial dose of study treatment, during treatment, or within 30 days of the last dose of treatment must be reported to the DF/HCC Overall Principal Investigator on the local institutional SAE form. This includes events meeting the criteria outlined in Section 10.1.2, as well as the following:

- Grade 2 (moderate) and Grade 3 (severe) Events – Only events that are unexpected and possibly, probably or definitely related/associated with the intervention.
- All Grade 4 (life-threatening or disabling) Events – Unless expected AND specifically listed in the protocol as not requiring reporting.
- All Grade 5 (fatal) Events – When the participant is enrolled and actively participating in the trial OR when the event occurs within 30 days of the last study intervention.

Note: If the participant is in long term follow up, report the death at the time of continuing review.

Participating investigators must report each serious adverse event to the DF/HCC Overall Principal Investigator within 24 hours of learning of the occurrence. In the event that the participating investigator does not become aware of the serious adverse event immediately (e.g., participant sought treatment elsewhere), the participating investigator is to report the event within 24 hours after learning of it and document the time of his or her first awareness of the adverse event. Report serious adverse events by telephone, email or facsimile to:

CONFIDENTIAL

This document is confidential. Do not disclose or use except as authorized.

[name], PhD
[contact]
[contact]
[REDACTED]

AND

[REDACTED]

AND

Novartis Pharmaceuticals Integrated Medical Safety Department
[REDACTED]

AND

FDA via MedWatch 3500A. Please fax to phone number listed on the MedWatch form

Within the following 24-48 hours, the participating investigator must provide follow-up information on the serious adverse event. Follow-up information should describe whether the event has resolved or continues, if and how the event was treated, and whether the participant will continue or discontinue study participation.

10.4.2 Non-Serious Adverse Event Reporting

Non-serious adverse events will be reported to the DF/HCC Overall Principal Investigator on the toxicity Case Report Forms.

10.5 Reporting to the Institutional Review Board (IRB)

Investigative sites within DF/HCC will report all serious adverse events directly to the DFCI Office for Human Research Studies (OHRS).

Other investigative sites should report serious adverse events to their respective IRB according to the local IRB's policies and procedures in reporting adverse events. A copy of the submitted institutional SAE form should be forwarded to:

[name], PhD
[contact]
[contact]
[REDACTED]

CONFIDENTIAL

This document is confidential. Do not disclose or use except as authorized.

The DF/HCC Principal Investigator will submit SAE reports from outside institutions to the DFCI Office for Human Research Studies (OHRS) according to DFCI IRB policies and procedures in reporting adverse events.

10.6 Reporting to the Food and Drug Administration (FDA)

The DF/HCC Overall Principal Investigator, as holder of the IND, will be responsible for all communication with the FDA. The DF/HCC Overall Principal Investigator will report to the FDA, regardless of the site of occurrence, any adverse event that is serious, unexpected and reasonably related (i.e., possible, probable, definite) to the study treatment.

Unexpected fatal or life-threatening experiences associated with the use of the study treatment will be reported to FDA as soon as possible but in no event later than 7 calendar days after initial receipt of the information.

All other serious unexpected experiences associated with the use of the study treatment will be reported to FDA as soon as possible but in no event later than 15 calendar days after initial receipt of the information.

Events will be reported to the FDA by telephone ([name]) or by fax ([name]) using Form FDA 3500A (Mandatory Reporting Form for investigational agents) or FDA Form 3500 (Voluntary Reporting Form for commercial agents). Forms are available at <http://www.fda.gov/medwatch/getforms.htm>.

10.7 Reporting to Hospital Risk Management

Participating investigators will report to their local Risk Management office any subject safety reports or sentinel events that require reporting according to institutional policy.

10.8 Monitoring of Adverse Events and Period of Observation

All adverse events, both serious and non-serious, and deaths that are encountered from initiation of study intervention, throughout the study, and within 30 days of the last study intervention should be followed to their resolution, or until the participating investigator assesses them as stable, or the participating investigator determines the event to be irreversible, or the participant is lost to follow-up. The presence and resolution of AEs and SAEs (with dates) should be documented on the appropriate case report form and recorded in the participant's medical record to facilitate source data verification.

For some SAEs, the study sponsor or designee may follow-up by telephone, fax, and/or monitoring visit to obtain additional case details deemed necessary to appropriately evaluate the SAE report (e.g., hospital discharge summary, consultant report, or autopsy report).

Participants should be instructed to report any serious post-study event(s) that might reasonably be related to participation in this study. Participating investigators should notify the DF/HCC Overall Principal Investigator and their respective IRB of any unanticipated death or adverse event occurring after a participant has discontinued or terminated study participation that may reasonably be related to the study.

11. DATA AND SAFETY MONITORING

11.1 Data Reporting

11.1.1 Method

The QACT will collect, manage, and monitor data for this study.

11.1.2 Data Submission

The schedule for completion and submission of case report forms (paper or electronic) to the QACT is as follows:

Form	Submission Timeline
Eligibility Checklist	Complete prior to registration with QACT
On Study Form	Within 14 days of registration
Baseline Assessment Form	Within 14 days of registration
Treatment Form	Within 10 days of the last day of the cycle
Adverse Event Report Form	Within 10 days of the last day of the cycle
Response Assessment Form	Within 10 days of the completion of the cycle required for response evaluation
Off Treatment/Off Study Form	Within 14 days of completing treatment or being taken off study for any reason
Follow up/Survival Form	Within 14 days of the protocol defined follow up visit date or call

11.2 Safety Meetings

The DF/HCC Data and Safety Monitoring Committee (DSMC) will review and monitor toxicity and accrual data from this trial. The committee is composed of clinical specialists with experience in oncology and who have no direct relationship with the study. Information that raises any questions about participant safety will be addressed with the Principal Investigator and study team.

The DSMC will meet quarterly and/or more often if required to review toxicity and accrual data. Information to be provided to the committee may include: up-to-date participant accrual; current dose level information; DLT information; all grade 2 or higher unexpected adverse events that have been reported; summary of all deaths occurring within 30 days for Phase I or II protocols; for gene transfer protocols, summary of all deaths while being treated and during active follow-up; any response information; audit results, and a summary provided by the study team. Other information (e.g. scans, laboratory values) will be provided upon request.

CONFIDENTIAL

This document is confidential. Do not disclose or use except as authorized.

11.3 Monitoring

Involvement in this study as a participating investigator implies acceptance of potential audits or inspections, including source data verification, by representatives designated by the DF/HCC Overall Principal Investigator (or Protocol Chair) or DF/HCC. The purpose of these audits or inspections is to examine study-related activities and documents to determine whether these activities were conducted and data were recorded, analyzed, and accurately reported in accordance with the protocol, institutional policy, Good Clinical Practice (GCP), and any applicable regulatory requirements.

All data will be monitored for timeliness of submission, completeness, and adherence to protocol requirements. Monitoring will begin at the time of participant registration and will continue during protocol performance and completion.

12. REGULATORY CONSIDERATIONS

12.1 Protocol Review and Amendments

This protocol, the proposed informed consent and all forms of participant information related to the study (e.g., advertisements used to recruit participants) and any other necessary documents must be submitted, reviewed and approved by a properly constituted IRB governing each study location.

Any changes made to the protocol must be submitted as amendments and must be approved by the IRB prior to implementation. Any changes in study conduct must be reported to the IRB. The DF/HCC Overall Principal Investigator (or Protocol Chair) will disseminate protocol amendment information to all participating investigators.

All decisions of the IRB concerning the conduct of the study must be made in writing.

12.2 Informed Consent

All participants must be provided a consent form describing this study and providing sufficient information for participants to make an informed decision about their participation in this study. The formal consent of a participant, using the IRB approved consent form, must be obtained before the participant is involved in any study-related procedure. The consent form must be signed and dated by the participant or the participant's legally authorized representative, and by the person obtaining the consent. The participant must be given a copy of the signed and dated consent document. The original signed copy of the consent document must be retained in the medical record or research file.

12.3 Ethics and Good Clinical Practice (GCP)

This study is to be conducted according to the following considerations, which represent good and sound research practice:

- E6 Good Clinical Practice: Consolidated Guidance
www.fda.gov/downloads/RegulatoryInformation/Guidances/UCM129515.pdf
- US Code of Federal Regulations (CFR) governing clinical study conduct and ethical principles that have their origin in the Declaration of Helsinki
 - Title 21 Part 11 – Electronic Records; Electronic Signatures
www.access.gpo.gov/nara/cfr/waisidx_02/21cfr11_02.html
 - Title 21 Part 50 – Protection of Human Subjects
www.access.gpo.gov/nara/cfr/waisidx_02/21cfr50_02.html
 - Title 21 Part 54 – Financial Disclosure by Clinical Investigators
www.access.gpo.gov/nara/cfr/waisidx_02/21cfr54_02.html
 - Title 21 Part 56 – Institutional Review Boards
www.access.gpo.gov/nara/cfr/waisidx_02/21cfr56_02.html
 - Title 21 Part 312 – Investigational New Drug Application
www.access.gpo.gov/nara/cfr/waisidx_02/21cfr312_02.html
- State laws
- DF/HCC research policies and procedures
<http://www.dfhcc.harvard.edu/clinical-research-support/clinical-research-unit-cru/policies-and-procedures/>

It is understood that deviations from the protocol should be avoided, except when necessary to eliminate an immediate hazard to a research participant. In such case, the deviation must be reported to the IRB according to the local reporting policy.

12.4 Study Documentation

The investigator must prepare and maintain adequate and accurate case histories designed to record all observations and other data pertinent to the study for each research participant. This information enables the study to be fully documented and the study data to be subsequently verified.

Original source documents supporting entries in the case report forms include but are not limited to hospital records, clinical charts, laboratory and pharmacy records, recorded data from automated instruments, microfiches, photographic negatives, microfilm or magnetic media, and/or x-rays.

12.5 Records Retention

All study-related documents must be retained for the maximum period required by applicable federal regulations and guidelines or institutional policies.

13. STATISTICAL CONSIDERATIONS

13.1 Study Design/Endpoints

CONFIDENTIAL

This document is confidential. Do not disclose or use except as authorized.

This study will enroll participants with ALK-rearranged, advanced (stage IIIB or IV) NSCLC with acquired resistance or intolerance to ALK TKI therapy. Participants will receive AUY922 on a weekly basis with radiographic assessments of response performed every 6 weeks. Response will be scored by RECIST version 1.1 criteria and consist of partial responses and complete responses. Treatment with AUY922 will continue until disease progression, unacceptable toxicity, participant withdrawal, death or discontinuation from the study for any other reason.

In order to investigate the preliminary efficacy of AUY922 in participants with acquired resistance or intolerance to ALK TKIs, the primary endpoint for this cohort is the best overall response rate using RECIST version 1.1 criteria. If at least 4 of 20 participants were to achieve a complete or partial response, AUY922 will be considered to have promising clinical activity in this molecularly defined population. The decision rule is associated with 89% power if 30% of participants in this population truly were to have tumors responsive to AUY922. In contrast, the probability of type 1 error is only 13% if the underlying rate of overall response were 10%, indicating a minimal level of anti-tumor activity.

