2.3.3.2 CAUY922A2206

The primary purpose of the ongoing study [CAUY922A2206] is to determine the efficacy of AUY922, administered intravenously on a once a week schedule at 70 mg/m², in adult patients with advanced NSCLC treated with at least two prior lines of chemotherapy. The study also assesses additional safety, tolerability and pharmacokinetic (PK) profile of AUY922 as secondary objectives. Patients in this study are stratified, retrospectively and prospectively, based on their molecular tumor etiology. All patients are required to have received at least one prior platinum containing regimen with the exception of patients harboring EGFR activating mutation tumors. The following strata are evaluated:

1. Patients with EGFR activating mutation tumors (Note: These patients must have progressed on one prior EGFR TKI containing regimen unless they have documented de novo resistance to EGFR TKI (e.g. T790M or exon 20 insertions))
2. Patients with *KRAS* mutant tumors
3. Patients with EGFR wt and *KRAS* wt tumors
4. Patients with EML4-ALK translocations

CONFIDENTIAL

This document is confidential. Do not disclose or use except as authorized.

5. A fifth stratum is evaluating EGFR mutant patients that are less heavily pre-treated (up to two prior lines), without CNS metastasis. This stratum is termed Modified EGFR mutant stratum

As of January 15, 2012, 118 patients were treated in this study. Of these, data for 114 patients has been entered in the clinical database (median age 60 years; 44% male; 86% adenocarcinoma; 28 patients KRAS mutant stratum [25%]; 35 patients EGFR mutant stratum [31%]; 31 patients EGFR/KRAS/ALK wt stratum [28%]; and 16 patients to the EML4-ALK stratum [28%]. Four patients could not be stratified due to insufficient tumor material submitted for analyses. Most patients were heavily pretreated: 61% had received ≥ 3 prior systemic regimens; 64% had WHO PS 1 or 2. Mean duration of exposure was 9.1 weeks (range 1-18+). The most frequent adverse events (AEs, any grade [Gr]) were diarrhea (73%), visual AEs (71%), and nausea (43%). Most AEs were Gr 1/2; Gr 3/4 AE's were rare (all <10%).

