13.2 Sample Size/Accrual Rate

Our estimated sample size is 20 participants. ALK translocations are identified in approximately 4-5% of patients with NSCLC. At MGH alone, approximately 500 patients with NSCLC undergo genotyping annually. Since a majority of these cases are likely to be ALK TKI naïve our study population is likely to be smaller. Across all participating institutions, we hope to enroll 1 participant per month.

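### Section 13.1 has no futility rule, although stopping accrual at 0 responses in the first 12 treated would barely change the stated power and type I error

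*Combined protocol and SAP*

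**What the plan says.** Section 13.1 defines a single-stage design. On the endpoint it says "the primary endpoint for this cohort is the best overall response rate using RECIST version 1.1 criteria", and on the decision, "If at least 4 of 20 participants were to achieve a complete or partial response, AUY922 will be considered to have promising clinical activity". It then gives the operating characteristics: "The decision rule is associated with 89% power if 30% of participants in this population truly were to have tumors responsive to AUY922", and "the probability of type 1 error is only 13% if the underlying rate of overall response were 10"%. Section 13.2 adds "Our estimated sample size is 20 participants" and, on accrual, "we hope to enroll 1 participant per month".

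Sections 13.1 to 13.4 contain no interim analysis, second stage or futility rule. Under section 11.2 the monitoring committee "will review and monitor toxicity and accrual data from this trial". That section also lists response information among the items the committee may receive, and lets it meet quarterly or more often. It attaches no response count and no action to that information.

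Four other passages bear on a possible look. Section 1.2.1 counts a response at any time after treatment. Scans are every 6 weeks. Sections 8.1.2 and 9 require responses to be confirmed 4 to 6 weeks later. Section 8.1.2 assigns RECIST assessment to central review, which need not be available in real time.

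**The concern.** Section 13.1 itself treats a 10% response rate as minimal activity. If the drug performs at or below that level, the plan still enrols all 20. After 0 responses in 12, success would need at least 4 responders among the last 8. That has probability 0.5% at a true rate of 10%.

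Up to 8 more people could therefore start weekly infusions in a trial that is unlikely to meet its own criterion. Section 2.3.3.2 reports diarrhea in 73% and visual events in 71% of patients on this drug, mostly grade 1 or 2, with grade 3/4 events rare and each under 10%. The question is whether a simple look could limit this without giving up the power and type I error that the plan relies on.

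**Working it through.** **Inputs.** From section 13.1: n = 20, success at 4 or more responders, null rate 0.10, alternative 0.30, scans every 6 weeks. From section 13.2: about 1 participant per month. The look at 12 is this review's proposal and is not in the documents.

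**Step 1. Reproduce the plan.** With X ~ Bin(20, p):
- P(X ≥ 4) at p = 0.30 is 0.8929, printed as 89%.
- P(X ≥ 4) at p = 0.10 is 0.1330, printed as 13%.

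**Step 2. Add a stop at 0 of 12.** The only successes lost are those with 0 responders in the first 12 and at least 4 in the last 8:

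P(success) = P(Bin(20, p) ≥ 4) − (1 − p)^12 × P(Bin(8, p) ≥ 4)

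- p = 0.30: 0.8929 − 0.01384 × 0.1941 = 0.8902
- p = 0.10: 0.1330 − 0.2824 × 0.0050 = 0.1315

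Power changes by −0.27 points and type I error by −0.14 points. Both still print as 89% and 13%.

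**Step 3. Benefit.** P(stop) = (1 − p)^12. If k participants enrol while the 12th awaits a scan, expected N = 20 − (8 − k) × P(stop).

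| True rate | P(stop) | Expected N, k = 0 |
|---|---|---|
| 5% | 0.540 | 15.7 |
| 10% | 0.282 | 17.7 |
| 30% | 0.014 | 19.9 |

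At 1 per month and a 6-week scan, k is 1 to 2. At a 10% rate, expected N is then 20 − 7 × 0.282 = 18.0 or 20 − 6 × 0.282 = 18.3.

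**Step 4. Late responses.** Step 2 assumes that every eventual responder among the 12 has been seen at the look. The documents do not say how early responses appear, so this is varied as an assumption. If each responder is visible with probability f, each participant shows no response with probability 1 − pf, and successes are lost when unseen responders plus the last 8 would have reached 4.

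*Rule limited to each participant's own first scan, true rate 30%:*

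| f | P(stop) | Power |
|---|---|---|
| 100% | 1.4% | 89.0% |
| 90% | 2.3% | 88.6% |
| 80% | 3.7% | 87.7% |
| 50% | 14.2% | 79.4% |

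*Rule counting every scan up to the 12th participant's first scan:* at 1 per month, participant 11 is then about 10 weeks in, with one scheduled scan. Participant 10 is about 14 to 15 weeks in, with two. Taking f = 50% for the last two and 100% for the other ten, power is 88.7% and P(stop) at 30% is 2.0%.

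**Step 5. Is 12 special?** No.
- Stop at 0 of 11: power 0.8876, type I error 0.1303, P(stop at 10%) 31%, expected N at 10% 17.2.
- Stop at 1 or fewer of 15: power 0.8878, type I error 0.1299, P(stop at 10%) 55%, expected N at 10% 17.3.
- Stop at 0 of 10: power 0.8830, which would print as 88%.

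**The case against.** A single stage of 20 is defensible. Section 2.4 reports partial responses to this drug in 3 of 11 crizotinib-treated patients (27%) and in 7 of 19 ALK-positive patients overall (37%). At 27%, the chance of 0 in 12 is 0.73^12 = 2.3%, so the rule would seldom act. Even at 10% it fails to stop 72% of the time and, with overrun, saves about 2 participants or fewer. The remaining participants also inform safety, disease control, survival and the molecular objectives. A real-time count would need prompt central reads, or a statement that local reads govern. All of this stands and limits the size of the point. The prior series are small, however, and do not exclude a low rate.

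A reader might also infer stronger claims that the documents do not support:
- *The trial has in effect failed at 0 of 12.* At the 30% design alternative, success still has probability 19%.
- *The look costs nothing.* That holds only if nearly all responses are visible at the look. Because the endpoint is response at any time, a rule tied to each participant's first scan could cost much more.
- *The committee cannot see efficacy.* Section 11.2 lets it receive response information. What is missing is a threshold and an action.
- *Participants face severe toxicity without oversight.* Section 2.3.3.2 describes mostly low-grade events, and section 11.2 provides toxicity review.

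**Conclusion.** The point holds as a cheap improvement. The plan contains no error or contradiction here, and its 89% and 13% are right for the rule it states. Section 13.1 omits a futility look that would leave power at 89.0% (from 89.3%) and type I error at 13.2% (from 13.3%). The power loss is about 0.3 points, or about 0.6 if half the responses of the last two participants are still unseen.

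The gain is modest: a 28% chance of stopping early at a 10% rate and 54% at 5%, against 1.4% at 30%. Expected enrolment at 10% is 17.7, or 18.0–18.3 with realistic overrun.

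These figures assume independent responses, accrual near 1 per month, a count that uses all available scans, and every stopped trial being scored as not meeting the 4-responder rule.

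**What to change.** Add to section 13.1:

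*If none of the first 12 treated participants has a CR or PR (confirmed or not) on any scan obtained up to the 12th participant's first scheduled post-baseline scan, accrual stops; otherwise enrol to 20 and apply the 4-responder rule.*

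Also state:
- whether the local or the central read governs the count;
- that the rule concerns accrual only;
- that a stop counts as not meeting the success criterion.

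In section 11.2, have the committee review the count when it is due and not at the next quarterly meeting. Each further enrolment during the wait adds 0.28 to expected N at a 10% rate.

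Counting unconfirmed responses avoids stopping while a confirmatory scan is pending. Waiting for confirmation would let about 2 to 3 participants enrol, not 1 to 2.

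The cost is a short amendment, one timely response count, 0.3 to about 0.6 points of power under the assumptions above, and less secondary-endpoint data if the trial stops. No accrual hold is required. If the sponsor prefers to keep a single stage, section 13.1 should say so and give the reason, for which the prior response data in section 2.4 are the natural basis.
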